4.4 Completion of Clinical Trial

A participant is considered to have completed the clinical trial if he/she has completed the Day 40 assessments as shown in [Table 3](#) - SOA.

The end of the clinical trial is defined as the date of last scheduled procedure shown in the SOA for the last participant in the trial.

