5.2 General Definitions

Variable	Definition
Study Day	
• Study Day = date of interest – reference date + 1, when the date of interest \geq reference date;• otherwise, Study Day = date of interest – reference date. 
Note: if either day is missing, reference date calculations will not be performed. Should imputation be performed, then Study day may be derived.

Baseline	Defined as the last non-missing value collected prior to receiving the first dose of study treatment (based on date and time of administration as applicable).
Post-baseline	Defined as values collected after receipt of the first dose of study treatment (based on date and time of administration as applicable)
Change from Baseline	Defined as: Post-baseline value – Baseline value

Percent Change from Baseline	Defined as: (Post-baseline value – Baseline value)/Baseline value x 100. Note: To compute percent change from baseline, the baseline value cannot be equal to zero.
Duration on Study	End of study date – randomization date +1.
Disease Onset	Self-reported start date of first COVID-19 symptom – date of first dose of study treatment. Time will be considered in the derivation if collected for both dates. If the self-reported date is missing, the date of positive COVID-19 test will be used.
Duration of Adverse Event (in days)	
 • Stop date of event – start date of event + 1, if time is not collected. • (Stop date/time of event – start date/time of event)/24, if time is collected.
Months	Divide by 30.4375
Year	Divide by 365.25
Week	Divide by 7

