6.2 Efficacy

Analyses and summary statistics will be reported on the mITT population. Efficacy endpoints are assessed up to Day 28. All data will be listed. Sensitivity and supplemental analyses may be repeated in other analysis populations.

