6.2.2.1 Continuous Endpoints

Descriptive statistics will be provided for each endpoint and will be reported by treatment arm. Endpoints that are not normally distributed will also display geometric means. Absolute values and changes from baseline will be presented for the following:

- Inflammation markers (COVID-19 Specific markers: eGRF, Troponin, CRP, Ferritin, D-dimer)
- WHO Ordinal Scale for Clinical Improvement

Baseline will be defined as the value in the database prior to receiving any amount of study treatment. Line plots of means with error bars for the above endpoints will be presented by treatment group. Figures of means for both absolute values at each timepoint and the changes from baseline will be provided.

Changes from baseline will further be analyzed statistically using a mixed model repeated measures (MMRM) analysis. Factors include treatment arm, timepoint, age (≤ 50 , >50 to 65 , >65) and number of co-morbidities (1, 2, 3+). The baseline value of the endpoint will be included as the covariate. Patient will be repeated by timepoint. An unstructured covariance and the Kenward Roger's approximation for the degrees of freedom will be assumed. Least-square means will be provided for the treatment differences (INB03 + SofC vs Placebo + SofC) as well as the corresponding 95% CIs.

Descriptive statistics will be provided for the following endpoints and reported by treatment arm.

- Length of stay in index hospital
- Days to disease progression

Length of stay in index hospital will be derived as the index hospital discharge date – randomization date +1. Time will be considered in the derivation if collected for both dates. If discharge date is missing, date of death or end of study date will be used, whichever comes first.

Days to disease progression is not a specified secondary endpoint in the clinical study protocol, however is of interest to summarize. Days to disease progression will be derived as the first date of disease progression – randomization date +1. Intercurrent events, as defined in Section 6.2.1.3, will be considered when assigning a patient as having disease progression. Patients with no disease progression and who have completed the study will be censored as the duration on study. Patients who terminated the study early and with no disease progression according to Section 6.2.1.3 will be censored and given the longest duration, 40 days.

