A multi-factor analysis of variance (ANOVA) will be used to assess the differences between treatment arms for each endpoint. Treatment arm, age (≤ 50 , >50 to 65 , >65) and number of co-morbidities (1, 2, 3+) will be included as factors in the model. Least-square means will be provided for the treatment differences (INB03 + SofC vs Placebo + SofC) as well as the corresponding 95% CIs. If assumptions for ANOVA are not met then a comparable non-parametric test will be performed (e.g., rank ANOVA or Wilcoxon rank-sum tests).

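### Days to disease progression is compared by ANOVA with early leavers scored at 40 days, so the censoring the SAP names has no effect on the result

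*SAP*

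**What the plan says.** SAP 6.2.2.1 adds days to disease progression to the protocol's secondary endpoints and counts them from randomization. Participants without progression get a number in one of two ways.

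- Completers: "Patients with no disease progression and who have completed the study will be censored as the duration on study". SAP 5.2 defines duration on study as "End of study date – randomization date +1". Under Protocol 4.4 a participant is a completer if "he/she has completed the Day 40 assessments".
- Early leavers: "Patients who terminated the study early and with no disease progression according to Section 6.2.1.3 will be censored and given the longest duration, 40 days". The value is the same whatever day they left.

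The same section goes on: "A multi-factor analysis of variance (ANOVA) will be used to assess the differences between treatment arms for each endpoint". The factors are arm, age group and number of co-morbidities. The output is least-squares mean differences with 95% CIs, and the fallback is a rank ANOVA or Wilcoxon test. Neither document plans a Kaplan-Meier, log-rank or Cox analysis.

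SAP 6.2.1.3 decides who counts as progressed. Loss to follow-up with no discharge date counts as progression. Withdrawals, losses after discharge and other discontinuations are judged on the last WHO ordinal score.

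**The concern.** A value is censored when the true time is known only to exceed it, and the analysis has to use that fact. ANOVA and rank tests do not, so every assigned number enters as an observed time to progression. For a participant followed to about Day 40 this does little harm, because the value was in effect observed. For an early leaver the 40 days are mostly unobserved. Any leaver who would have progressed later is scored as if he or she had not.

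At stake are the mean difference, its CI and the nominal p-value for this endpoint. They mix the drug's effect with differences in dropout between arms. The sign of the error depends on which date counts as end of study, which the SAP does not fix.

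**Working it through.** The documents give no power or effect size for this endpoint, so there is no plan figure to reproduce.

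**1. What each participant scores**

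| Participant | Last observed day | Score | Unobserved credit |
|---|---|---|---|
| Leaves Day 2, not classed as progressed | 2 | 40 | 38 |
| Leaves Day 3, same | 3 | 40 | 37 |
| Leaves Day 10, same | 10 | 40 | 30 |
| Lost, no discharge date | any | progression | none |
| Completer, end of study at Day 40 visit (±2 days, Schedule of Assessments) | 38 to 42 | 38 to 42 | none |
| Completer, if end of study is the Day 70 contact | about 70 | about 70 | progression assessed only to Day 40 |

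A completer seen on Day 38 or 39 therefore ranks below a Day 3 leaver.

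**2. From credit to bias.** The credit is not itself the bias: a leaver who would never have progressed would have scored about 40 anyway. With no drug effect and completers at 40 days, the spurious gain for the arm with more dropout is

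bias = x × r × (40 − t),

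where x is the excess dropout, r the share of those extra leavers who would have progressed after leaving, and t their mean progression day.

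*Non-informative dropout.* Assumptions not in the documents: progression times exponential with mean 6 days (rounded up, capped at Day 28) and departures spread evenly over Days 2 to 8. The 21% progression in both arms is the SAP's placebo rate.

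- The chance that a progressor is still event-free at departure is the mean of exp(−d/6) over d = 2 to 8: (0.717 + 0.607 + 0.513 + 0.435 + 0.368 + 0.311 + 0.264)/7 = 0.459.
- r = 0.21 × 0.459 = 0.096, and t is about 10.7.
- 15% versus 5%: 0.10 × 0.096 × 29.3 = 0.28 day. Simulation (1,000 replicates) gave 0.40 with 38 per arm and 0.26 with 173 per arm, Monte Carlo errors about 0.10 and 0.05.
- 30% versus 5%: 0.25 × 0.096 × 29.3 = 0.70 day. Simulation gave 0.85 and 0.64.

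*Informative dropout.* Assume x = 0.10 and t = 5. With r = 0.5 the bias is 0.10 × 0.5 × 35 = 1.75 days; with r = 0.2 it is 0.10 × 0.2 × 35 = 0.7 day.

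**3. If end of study is Day 70.** A leaver who would never have progressed now loses 30 days against a completer: bias = x × (−0.79 × 30 + 0.096 × 29.3) = x × (−23.7 + 2.8).

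- 15% versus 5%: −2.1 days (simulated −2.0 and −2.2).
- 30% versus 5%: −5.2 days (simulated −5.4 and −5.2).

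**4. False-positive rates at a nominal two-sided 5%**, no true effect, two-sample t-test standing in for the ANOVA:

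- Day 40 end, 38 per arm (77 dosed, split about evenly): 5% to 6%.
- Day 40 end, 173 per arm: about 6%, rising to about 10% only at 30% versus 0% dropout.
- Day 70 end, both arm sizes: ANOVA 8% to 48%, Wilcoxon 8% to 84%.
- Log-rank with censoring at dropout, all scenarios: 4% to 7%.

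The low rates under a Day 40 end make sense. With mean progression at about Day 6.5, the SD is roughly √(0.21 × 0.79) × 33.5 = 13.7 days. The standard error at 38 per arm is then 13.7 × √(2/38) = 3.1 days, far above a 0.3-day bias.

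**5. Does censoring at last contact remove it?** Take the 1.75-day case with 20% progressing overall and departures before any progression. Of 100 participants, 10 leave, 5 of them future progressors, so the observed risk is 15/90 = 16.7%. The remaining spurious gain is (0.200 − 0.167) × 35 = about 1.2 days. Informative dropout is only partly dealt with.

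**The case against.** The strongest reply is that little depends on this endpoint. The SAP itself says that it is not a protocol endpoint and is there to be summarized; p-values are nominal, and the primary test, its alpha and the futility rule do not use it. For anyone followed to Day 40, time capped at 40 days is a legitimate restricted progression-free time. All of this stands and limits the severity. It does not remove the fault, because the section still prescribes between-arm means, CIs and tests.

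A reader might infer more than the documents support:

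- *Every dropout scores as a best outcome.* No. Loss without a discharge date counts as progression, and other leavers are first judged on their last WHO score.
- *The rule always rewards the arm with more dropout.* Only if completers end at about Day 40. That is the more natural reading, given the completion definition and the SAP's own reference to 40 days as the longest duration. But participants are contacted until Day 70, and the SAP does not say which date ends the study.
- *Most values are invalid, because 79% of placebo and 93% of INB03 participants are expected not to progress.* Those shares do not measure the fault. It lies in the early leavers, whose number is not given.
- *Anything past Day 28 is outside the data.* SAP 6.2 does say "Efficacy endpoints are assessed up to Day 28", but Protocol 7.2.1 and the Schedule of Assessments follow progression to Day 40. The real gap is that the SAP does not say how a progression on, for example, Day 33 is scored.

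**Conclusion.** The point holds. Non-progressors are called censored, but the planned comparison cannot use censoring, and early leavers not classed as progressed receive up to 38 days that nobody observed. The direction of the bias depends on an end-of-study date that needs to be fixed.

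Under a Day 40 end and assumed non-informative dropout of 15% versus 5%, the bias is about 0.3 to 0.4 day, with the false-positive rate close to nominal at about 38 per arm. It is larger if leavers are at higher risk of progressing. The 1.75-day figure illustrates this, but rests wholly on assumed inputs and is not an estimate for this trial. Under a Day 70 end the bias is about −2 to −5 days in the scenarios tried. Because the endpoint is an SAP addition with nominal p-values and the primary analysis is untouched, this is a minor-to-moderate correction.

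**What to change.** In SAP 6.2.2.1, for days to disease progression only:

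- Delete the 40-day rule and the ANOVA and rank comparison. Use Kaplan-Meier curves, a log-rank test stratified as in the primary analysis, and a Cox hazard ratio. With 77 dosed, collapse strata as SAP 6.2.1.2 already allows.
- Censor participants without progression at the last date they were known to be progression-free.
- Set one common horizon: Day 28, to match the primary endpoint and SAP 6.2. Data to Day 40 can be shown as a supplement.
- Date the events imputed for loss without a discharge date at last contact, in line with SAP 6.2.1.3.
- State which date is the end-of-study date in SAP 5.2, since duration on study depends on it.
- Add a sensitivity analysis for informative dropout, because the new methods assume independent censoring and would leave part of that bias in place.

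The cost is SAP wording and standard programming on dates already collected. The SAP allows amendment before final database lock and unblinding. What is lost is the single difference in mean days, and Day 29 to 40 events move to the supplement.

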6.2.2.2 Binary Endpoints

Binary secondary endpoint will be summarized with number and percentage of patients with the criteria. The denominator for percentages will be the patients included in the treatment arm for the mITT population who have data for the endpoint. The following endpoints assessed up to Day 28 visit will be summarized by treatment arm:

- Proportion with 1 point, 2 point etc. increase/decrease in WHO Ordinal Scale
- Proportion with all-cause mortality at any time
- Proportion who transfer to ICU level care
- Proportion with a new onset of neurological disease
- Proportion with evidence of new CHF or new MI requiring medical intervention
- Proportion with new onset of embolus or thrombus
- Proportion who develop need for renal replacement therapy

Data on endpoints are directly captured in the eCRF. In the case of intercurrent events, the treatment policy strategy will be considered and the last-available record in the EDC prior to or on Day 28 will be used for reporting these events.

The statistical analyses for secondary endpoints with binary outcomes will be performed using CMH tests similar to the primary estimator.

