5.4 Handling of Withdrawal or Termination

Participants withdrawing from the study will be encouraged to complete the same final evaluations as participants completing the study according to this protocol (Day 40 assessments).

Reasonable efforts will be made to contact participants who are lost to follow-up. Investigator will be expected to try as much as possible to re-connect those participants at the end of the trial in order to obtain at least their vital status. These efforts must be documented in the participant's file.

Investigators will be trained about the importance of participant retention and steps to prevent missing data.

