6.2.1 Primary Efficacy Endpoint and Analyses

The primary objective of the study is to evaluate the effect INB03 + SofC has on disease progression compared with placebo + SofC. Disease progression is defined as death or requirement for mechanical ventilation in participants with pulmonary complications from COVID-19 infection. The primary endpoint to assess the objective is to compare the proportion of patients who reach disease progression in both treatment arms. Disease progression will be assessed up to Day 28. Patients will be identified as follows:

1 = Disease progression – defined as developing the need for mechanical ventilation or death by Day 28. Mechanical ventilation includes CPAP, BIPAP, or mechanical ventilation requiring intubation.

0 = No disease progression – defined as not developing the need for mechanical ventilation or death by Day 28

The null hypothesis is that there is no difference in the proportion of patients who have disease progression between treatment groups and the alternative is that the proportion of INB03 treated patients with disease progression is less than the proportion of placebo patients with disease progression.

$$H_0: P_{INB03} = P_{Placebo} \text{ vs } H_1: P_{INB03} < P_{Placebo}$$

Statistical analysis of the primary endpoint will be performed with a one-sided level of significance and final alpha of $\alpha=0.005$.

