6.2.1.3 Handling Missing Data

The following intercurrent events may lead to missing data for the primary endpoint. Imputation will be performed when the primary endpoint of mechanical ventilation or death information prior to Day 28 is missing.

Intercurrent Event	Strategy	Method of handling missing data
Withdraw consent prior to Day 28	While on treatment – data prior to event is of interest	the last available post-randomization record of the WHO Ordinal Scale for Clinical Improvement, prior to the intercurrent event, will be used to assess disease progression
Lost to Follow-up prior to Day 28 with no hospital discharge date	Composite variable – event is considered informative about patient's outcome	the participant will be considered to have disease progression
Lost to Follow-up prior to Day 28 with a hospital discharge date	Treatment policy – data is used as if event never occurred	the last available post-randomization record of the WHO Ordinal Scale for Clinical Improvement, prior to the intercurrent event, will be used to assess disease progression
Discontinued from study for reasons other than Withdrawal of consent or Lost to Follow-up prior to Day 28	Treatment policy – data is used as if event never occurred	the last available post-randomization record of the WHO Ordinal Scale for Clinical Improvement, prior to the intercurrent event, will be used to assess disease progression
Did not receive mechanical ventilation due to unavailability	Hypothetical – data is used assuming event did not occur	the last available post-randomization record of the WHO Ordinal Scale for Clinical Improvement, prior to the intercurrent event, will be used to assess disease progression

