7.2 APPENDIX 2: Estimand Terminology

Source: ICH E9 R1

Strategy	Description
Treatment policy	The occurrence of the intercurrent event is irrelevant: the value for the variable of interest is used regardless of whether or not the intercurrent event occurs.
Composite Variable	The occurrence of the intercurrent event is taken to be a component of the variable, i.e. the intercurrent event is integrated with one or more other measures of clinical outcome as the variable of interest.
Hypothetical	A scenario is envisaged in which the intercurrent event would not occur: the value to reflect that scientific question of interest is that which the variable would have taken in the hypothetical scenario defined.
Principal stratum	The target population might be taken to be the principal stratum (see Glossary) in which an intercurrent event would not occur.
While on treatment	Response to treatment prior to the occurrence of the intercurrent event is of interest.

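### Mortality and the other binary secondary endpoints carry a leaver's last record forward to Day 28 under a treatment-policy label, with an unclear denominator and no sensitivity analysis

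*SAP*

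**What the plan says.** SAP 6.2.2.2 covers the binary secondary endpoints up to Day 28, including all-cause mortality, ICU transfer, neurologic disease, CHF or MI, thromboembolism and renal replacement. It states: "In the case of intercurrent events, the treatment policy strategy will be considered". It then puts this into practice as follows: "the last-available record in the EDC prior to or on Day 28 will be used for reporting these events". The same section sets the denominator: "The denominator for percentages will be the patients included in the treatment arm for the mITT population who have data for the endpoint". Protocol 9.5.2 leaves the handling of intercurrent events for secondary endpoints to the SAP, so this is the only rule written for these endpoints. The general default in SAP 5.3 is not to impute.

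SAP Appendix 2 describes treatment policy in these words: "the value for the variable of interest is used regardless of whether or not the intercurrent event occurs".

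The primary endpoint is "defined as developing the need for mechanical ventilation or death by Day 28". Where that information is missing, SAP 6.2.1.3 has two kinds of rule:

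- **Lost before Day 28 with no hospital discharge date:** "the participant will be considered to have disease progression".
- **Withdrawal of consent, loss after discharge, or other discontinuation:** the last WHO ordinal record "prior to the intercurrent event, will be used to assess disease progression".

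The tipping point analysis in SAP 6.2.1.4 is for the primary endpoint only. For participants lost to follow-up, Protocol 5.4 asks sites to try to re-establish contact at the end of the trial, "in order to obtain at least their vital status".

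**The concern.** Treatment policy needs the Day 28 outcome whatever happened in between. Taking an earlier record as the Day 28 answer replaces unobserved time with an assumption of no event. The unobserved stretch can be long: Protocol 4.1 expects no contact between discharge and the Day 28 visit, so for someone discharged and then lost, the last record may date from discharge.

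The assumption also differs from the one made in the primary analysis. For a participant lost with no discharge date, SAP 6.2.1.1 calls the loss informative about outcome and SAP 6.2.1.3 imputes progression. In SAP 6.2.2.2 the same loss adds no death, ICU transfer or dialysis unless one was already recorded. By contrast, SAP 6.2.2.1 does import the 6.2.1.3 rules for days to disease progression.

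Mortality is the first-listed secondary endpoint and one component of the primary. If losses differ between arms, carry-forward favours the arm that loses more. The primary and mortality results could then diverge because of the dropout rules alone.

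**Working it through.** The plan states no figure for the binary secondary endpoints, so there is none to reproduce. The check has three parts.

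**1. One loss in hospital, no discharge date, no event recorded**

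Input: 77 participants dosed (SAP 6.2.4). Assumption: an even split under 1:1 allocation, 77 / 2 = 38.5 per arm.

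| Endpoint | Rule | Contribution to that arm |
|---|---|---|
| Disease progression | SAP 6.2.1.3, imputed event | 1 / 38.5 = 2.6 points |
| Mortality and each complication | SAP 6.2.2.2, last record | 0 / 38.5 = 0 points |

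**2. Two readings of the denominator**

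Assumed example for one arm: 38 dosed, 35 followed to Day 28 with 4 deaths, and 3 lost while alive.

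- Leavers kept and carried forward: 4 / 38 = 10.5%.
- Leavers excluded as having no data: 4 / 35 = 11.4%.
- Limits for the true rate: 4 / 38 = 10.5% if none of the three died, and (4 + 3) / 38 = 18.4% if all did.

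The two readings differ by 0.9 points, and neither conveys the upper limit.

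**3. Size of the carry-forward bias in mortality**

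Let m be the Day 28 death risk among those followed, d the share who leave alive with no later information, and k the risk in leavers relative to m.

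- Carry-forward rate = (1 − d) × m
- True rate = (1 − d) × m + d × k × m
- Shortfall = d × k × m

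The documents give none of these values. Assumed ranges: m 5% to 10%, d 2% to 10%, k 1 to 3.

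| m | d | k | Carry-forward | True | Shortfall |
|---|---|---|---|---|---|
| 5% | 2% | 1 | 4.9% | 5.0% | 0.1 points |
| 10% | 5% | 2 | 9.5% | 10.5% | 1.0 points |
| 10% | 10% | 3 | 9.0% | 12.0% | 3.0 points |

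In this model, excluding leavers returns m, which is 10.0% in the last row. That differs from carry-forward but is still below the true 12.0%.

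Suppose there is no drug effect, m = 10%, k = 1, and losses of 2% in one arm and 10% in the other. Carry-forward gives 0.98 × 10% = 9.8% against 0.90 × 10% = 9.0%. The true rate is 10.0% in both arms, so the 0.8-point gap comes only from unequal loss.

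**The case against.** Several objections have force.

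- **Denominator.** Restricting percentages to participants with data, together with the SAP 5.3 default against imputation, could mean that leavers without Day 28 status drop out. This stands as an ambiguity. It does not rescue the plan, because the SAP does not choose between readings that give different rates.
- **Events before leaving.** A reader might infer that everyone who leaves early counts as alive and free of complications. The documents do not support that: an ICU transfer, stroke, MI, thrombus or dialysis recorded before departure is kept. Only leavers with no recorded event are affected.
- **Conflict with the primary.** A reader might infer that the two analyses contradict each other. They do not in logic: progression is ventilation or death, and the composite strategy does not assert a death. Under SAP 6.2.1.3 the imputed failure applies only to loss without a discharge date; for other leavers the primary also uses a last record. One sentence in Protocol 9.5.1 would extend imputed failure to participants discharged without data to Day 28, but its next bullet and the SAP use the last WHO record, and the SAP is followed here. What remains is two different assumptions about the same missing data.
- **Deaths learned late.** A reader might infer that a death by Day 28 discovered at the end-of-trial contact is discarded. The documents do not say so. Protocol 7.2.1 asks for the date of death, and the Day 28 limit can be read as the event date. The SAP should still say which date governs.
- **Few losses.** Inpatients are assessed daily, and SAP 6.2.4 says randomized participants were followed to study completion. Losses may be few, but no count is given.
- **Censoring.** Kaplan-Meier assumes that those lost carry the same risk as those who remain. This is correct, so censoring alone is not enough.
- **Stakes.** Secondary p-values are nominal (SAP 6.2.2 and 6.2.5), and the primary test is untouched.

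**Conclusion.** The point holds in a limited form. SAP 6.2.2.2 applies a last-observation rule under a treatment policy label that does not fit the SAP's own definition. It leaves the denominator open. For participants lost without a discharge date, it assumes the opposite of what the primary analysis assumes, and nothing tests that choice.

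The size depends on how many were lost, which the documents do not report. Each inpatient loss moves that arm's progression rate by about 2.6 points and its mortality by 0, given an even split of the 77 dosed. Under the assumed ranges above, carry-forward understates mortality by 0.1 to 3.0 points. A reader might multiply the 2.6 points by several losses and conclude that mortality is badly understated; nothing in the documents supports a particular number of losses or of unrecorded deaths. The consequence is for the interpretation of mortality and complications, not for the primary test.

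**What to change.** Amend SAP 6.2.2.2 as follows.

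1. Count any event, and in particular any death, dated on or before Day 28 whenever it was learned, including through the end-of-trial vital-status contact.
2. Do not score unknown Day 28 status as a non-event. Estimate Day 28 mortality by Kaplan-Meier, censoring at the date last known alive. Where event dates are collected, estimate the other events by cumulative incidence with death as a competing event.
3. Add a sensitivity bound that counts participants lost in hospital without a discharge date as events. This matches the primary rule and is needed because censoring assumes non-informative loss.
4. Tabulate unknown Day 28 status by arm.

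The CMH test can stay alongside with nominal p-values, provided its denominator is stated and the treatment policy label is removed or made true.

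The cost is SAP wording, a little more programming and slightly wider intervals. Date of death is already requested (Protocol 7.2.1); availability of dates for the other events should be confirmed against the CRF. The SAP introduction allows amendment before final database lock. After that point, the change can be described and justified in the clinical study report, as SAP 1.1 provides.
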